6.6.4 Additional exploratory endpoints

For all exploratory endpoints as described in 4.2.4, descriptive presentations will be made and the change from Visit 7 to Visit 10, Visit 9 to Visit 10, Visit 10 to Visit 12, and Visit 1 to Visit 12 will be evaluated descriptively. No plots will be created, and no statistical analysis done.

These presentations include the endpoints as mentioned above in sections 6.6.1, 6.6.2, and 6.6.3 that will be presented as exploratory using only descriptive statistics for the Extension phase on data collected after Visit 10. For EQ-5D-5L as well as the EQ-5D-Y, a different questionnaire could be used between Visits 10 and 12 if a patient turns 18 before Visit 10, and for this reason separate QoL presentations will be created for Extension phase II, using Visit 10 measurements as baselines. The EQ-VAS score will be summarized by visit using descriptive statistics in a combined manner for patients aged < and ≥ 18 years (using Visit 10 age values).

For presentations on efficacy data collected after Visit 10, no imputations or LOCF is considered necessary.

6.6.5 Other additional statistical analyses

No other additional statistical analyses are foreseen.

6.7 Safety and tolerability evaluation

The safety and tolerability evaluation for the extension study is similar to what is described for the Parent study (see Section 5.7), with the remark that the evaluation is limited to the Extension phase only and Visit 7 is considered the baseline. For the AE presentation per treatment cycle, the cycles for Extension phase are as follows:

- Treatment cycle Extension phase I: the period between start of first treatment at Visit 7 and 24 hours after last dose at Visit 9.
- Washout cycle Extension phase I: starts 24 hours after last dose at Visit 9 until and includes Visit 10.
- Treatment cycle Extension phase II: the period between start of first treatment at Visit 10 and 24 hours after last dose at Visit 12.
- No washout cycle is defined for Extension phase II.

Note that for those patients that do not transition seamlessly to the Extension phase, additional prior medication/adverse events may be collected at the start of the Extension phase, and these will be presented separately from the prior medication/adverse events of the Parent phase.

Physical examination, which is collected twice during the Extension phase, will be presented as follows: general physical examination data will be tabulated and listed per visit. The summary table will include number/percentage of patients with normal or abnormal observations and NCS/CS frequencies/percentages for abnormal observations per visit.

6.8 Scheduled visits, dosing, and treatment compliance

The presentation for the Extension phase is similar to what is described for the Parent study phase (see Section 5.8), with the remark that the evaluation is limited to the Extension phase only and Visit 7 is considered the baseline.

7 CHANGES TO PROTOCOL AND OTHER RELEVANT REMARKS

Instead of Bland-Altman analyses of outcome scores at Visit 1 vs Visit 2, Visit 3 vs Visit 4, and Visit 5 vs Visit 6 as described in the protocol for the Parent study, an ICC method for agreement

Clinical Study Reference: IB1001-202

between the visits will be used instead to assess the stability of the outcome, as described in section 5.6.4. This is because no per-rater information is available in the dataset to be received, only an averaged or agreed value.

Regarding CI-S, the protocol is stating that for each assessment, the videos will be labeled as Video A, B, C, D, E, F. This is however not present in the DTA and test data from and is therefore removed from the SAP.

For Quality-of-Life measures, since the scoring is done for children with the EQ-5D-Y and for adults with the EQ-5D-5L, tabulations and analyses will be done separately for the corresponding age groups. The presentations on the VAS will be combined for children and adults.

For the Parent phase, sparse PK sampling will be collected for biochemical analysis to characterize the pharmacokinetics of N-Acetyl-L-Leucine in patients with GM2 Gangliosidosis. For the Extension phase, full PK profiles will be collected at Visit 7 and Visit 9. Creation of descriptive displays and reporting of these data is outside the scope of this statistical analysis plan. PK concentration data and PK parameters (following a population PK analysis) will be included in SDTM domains, after receipt. For the Parent phase a listing of PK concentration data will be created for inclusion in the Parent phase CSR, since the full PK report will only be available after the end of the Extension phase. Furthermore, urine tests for N-Acetyl-D-Leucine are handled by the same lab but will be included in the clinical database and will therefore be part of the CDISC datasets.

Regarding the sensitivity analysis (imputation of value -1) for missing data in the primary and secondary analyses: this is only applied to the primary analysis of the Parent phase. Regarding the LOCF/assumption of value 0 for missing data: this is only applied to the primary and one key secondary endpoint as specified in the relevant sections in this SAP.

The investigation of the intra-rater correlation cannot be performed, since the **sector** data do not differentiate the data per rater but rather provide an average or agreed value. Therefore, this analysis has been removed from the SAP.

Considering the primary endpoint of the Extension phase is a different one then the primary endpoint of the Parent Study, the trial is called successful only when the primary endpoint of the Parent Study is positive. All analyses of the Extension phase on data collected until Visit 10 are considered secondary to ones of the Parent Study. All presentations in the Extension phase on data collected after Visit 10 are exploratory and descriptive.

The analysis on ASIS as described in the protocol has been removed from the SAP, as there are too limited datapoints available to perform the analysis.

For some patients, repeat visits were scheduled if measurements could not be fully handled during the agreed visit. Repeat visits will be listed for BDRM, and during BDRM or Clean File meeting it will be decided how the repeat data will be handled for analysis. Decisions will be documented prior to Database lock.

The addition of a short section of Covid-19 details (with reference to an addendum) has been added to the SAP and is not mentioned in the protocol.

Clinical Study Reference: IB1001-202

8 COVID-19 DETAILS

This study is conducted during the COVID-19 outbreak. The following data capture decisions have been taken due to national, local, or site-specific restrictions imposed due to COVID-19, with the primary need to prioritize the safety of clinical study teams and patients, and to maintain the integrity of the study/data collection.

- All protocol deviations relating to COVID-19 are collected.
- If Visit 2 is performed 8 weeks (56 days) or more after Visit 1, some Visit 1 assessments must be repeated.
- Visits 3 and 5 can be converted to remote visits (i.e. phone, video conference).
- Visits 4 and 6 can be postponed until the in-person visit is feasible and should be performed in person. Where applicable, remote data collection should be collected on the date of the original visit. The postponed Visits 4 and 6 will collect all data per protocol.
- For the Extension Phase, no remote visits are allowed.

Currently, the impact of COVID-19 on the proposed statistical analyses is unknown. The statistical analysis already allows some flexibility for handling missing data, however, specific items/changes related to COVID-19 are being detailed in a separate document (Addendum 1), which will be maintained as a living document throughout the study continuation and adjusted based on the duration and extent of the impact of the COVID-19 situation.

9 DATA RECEIPT

All clinical eCRF data received from the Data Management provider per transfer agreement will be mapped to SDTM files. The information regarding minor/major violations will be received as excel file (a so-called "protocol deviations log") and will be transferred to SDTM as well. The blinded results on the video-recordings (blinded rater's CI-CS and CI-S) will be received from as provider following the transfer agreement and will be mapped to SDTM. The received data will include relevant categorizations on missing data.

The SDTM files will be recoded to ADaM format, where necessary. Listings will be programmed on the SDTM and ADaM datasets, statistical analyses, tables, and figures will be programmed on ADaM datasets.

For all received data, a split will be made between data for the Parent study and the data for the Extension phase, to allow submission of the CDISC data and documentation for the Parent study.

10 TECHNICAL DETAILS

10.1 Programming conventions

Programming conventions apply to both the Parent study as well as the Extension phase, unless otherwise specified.

Demographics

BMI will be calculated in SAS as follows: weight/height², with weight in kg and height in meter (unit kg/m²). Durations will be programmed as stated in the respective analysis sections. Where applicable, weight and height measurements will be converted to units cm and kg, using the following conversion factors: from inch to cm: multiply by 2.54, from lb to kg: multiply by 0.45359237. Variables with values representing a missing observation (such as -99, 99, 888 or 999) will be recoded to missing in SAS.

Intra BIO

Clinical Study Reference: IB1001-202

GM2 Diagnosis

Time since diagnosis will be calculated as the difference in days between first dose date and the date of diagnosis +1. Date of diagnosis will be taken as the earliest date from the following two records: the (earliest) date of Medical History with MHDECOD= "Tay-Sachs disease" or "Sandhoff disease" and the date of genetic confirmation of disease as recorded in the Primary Genetic Diagnosis of GM2 Gangliosidosis data.

If considered more feasible, the duration may be presented in weeks (calculated time divided by 7), months (calculated time divided by 365.25/12) or years (calculated time divided by 365.25) instead of days. For historical data however, it is likely that partial dates are available. If date of diagnosis is (partially) missing, the following will be applied:

- If only day is missing, the first day of the month will be used.
- If day and month are both missing, 1 January of the same year will be used.

If full date is missing, no imputation will be done.

Age calculation

Age at diagnosis will be based on the date of diagnosis (see above for determination) and the birth date as collected in the database. For a partial missing date of diagnosis, the rules as stated above will be applied. For partially missing birthdate: depending upon the level of precision of the collected birth date: if only month and year is available, then imputation of day 15 is used for calculation of age. If only birth year is available, 15 June of that year will be used as birthdate.

Age is not collected during the Extension phase, and therefore whenever age is necessary for any calculations or presentations at Extension phase visits, it should be calculated using the respective visit date combined with the date of birth as collected at Visit 1. The same imputation rule as stated above (for calculation of age at diagnosis) will be applied.

Blinded data

The blinded results on the video-recordings (blinded rater's CI-CS and CI-S) will be received from according to the agreed transfer specifications. Recoding needs to be done using the visit schedule provided with the blinded results, since the visit review order is randomly assigned. The LOCF for video comparison is already available in the data.

SCAFI

For 8MWT, assistance of another person or using the wall as support is not allowed. However, timed 8MWT trials for participants who used "unallowable support" (another person or the wall) are entered in the database, considering these measurements are also necessary due to their relation to the primary and a number of secondary endpoints of the study based on videos of the test. Therefore, for the SCAFI analysis, the data for these patients that used either the wall or person support during the 8MWT should be made missing.

Furthermore, patients for 9HPT, the following clinical rules apply:

- if proband cannot complete trial in 5 minutes (i.e. 300 seconds) with dominant hand, move on to the trials with non-dominant hand
- if proband cannot complete one trial in 5 minutes (i.e. 300 seconds) with non-dominant hand, discontinue 9HPT

As a consequence, if in the database values >300 are entered for Trial 1 and/or 2, the approach for handling these data in regards to SCAFI will be:

Clinical Study Reference: IB1001-202

- In the case Trial 1 has a value <300 and Trial 2 has a value of >300 seconds, only the trial 1 with value <300 will be used for further analysis.
- In the case Trial 1 has a value of >300 seconds and Trial 2 has a value of <300 seconds, the data will count as missing and unable to perform due to physical limitations (as per the discontinuation rules defined above, Trial 2 should not have been conducted)
- In other instances, where only one trial is performed with a value >300 seconds, or two trials are performed with both values >300 seconds, the data will be considered missing due to physical limitations and replaced with a missing value for further analysis.

After the adjustments made for 8MWT and 9HPT as above, SCAFI total score will be calculated as follows:

The mean of the trial1 and trial2 scores are determined for each subtest/hand, and referred to as: $8MW_avg$, $9HPT-D_avg$, $9HPT-ND_avg$ and $PATA_avg$. In case a subtest is only performed once, this value is taken as the mean. Then, the 8MW and 9HPT performance times are converted to the same dimension as the PATA rate, as follows: $8MW_recipr = 1/8MW_avg$, $9HPT_recipr = (1/9HPT-D_avg + 1/9HPT-ND_avg)/2$. Note that 8MW and 9HPT performance times cannot be 0.

Then each is converted into a Z-score using the following algorithms:

- 8MW_zscore = (8MW_recipr BL(mean 8MW_recipr)) / BL(SD 8MW_recipr)
- 9HPT_zscore = (9HPT_recipr BL(mean 9HPT_recipr)) / BL(SD 9HPT_recipr)
- PATA zscore = (PATA avg BL(mean PATA avg)) / BL(SD PATA avg)

where BL means baseline value and SD means standard deviation. The mean 8MW_recipr and SD 8MW_recipr are determined using the SAF analysis population.

In case of missing values, the following applies:

- The cases with either 8MW, 9HPT (in one or both hands) or PATA tests not performed at all ("unable to perform due to physical limitations" or "not performed for other reason") are excluded from the calculation of baseline means.
- Only when an 8MW score, 9HPT score or PATA score is missing due to "unable to perform due to physical limitations", then a substitution will be applied as follows:
 - $\circ~$ When 8MW tests were not performed, then 8MW_recipr will be substituted by 1/1800~s.
 - When 9HPT tests were not performed: if only data for one hand is missing, then 9HPT_avg=3000 s for that specific hand; when data for both hands are missing, then 9HPT_recipr=1/3000 s.

• When PATA tests were not performed, then PATA_avg is substituted with 0. For agreement on "unable to perform due to physical limitations" or "not performed for other reason", the sponsor will be contacted. The missings created for 8MWT and 9HPT as stated above are considered "unable to perform due to physical limitations".

According to the "SCAFI rating manual", the SCAFI total score is to be determined as the arithmetic mean of the 3 Z-scores. However, following explanation of IntraBio and [name], the SCAFI score needs to be calculated as the mean of the non-missing Z-scores. The SCAFI score can only be determined if at least one test is actually performed, i.e. in case all tests were imputed because of missing values, no SCAFI score will be determined. This contradicts the "SCAFI rating manual".

SARA

Clinical Study Reference: IB1001-202

The overall SARA score is reported as provided in the eCRF. For presentation of the subscore results, the individual results as provided in the eCRF will be used, where for the subscores finger chase, nose-finger test, fast alternating hand movements, heel-shin slide this is the average value for the two sides (left and right) as determined per eCRF.

mDRS

The mDRS composite score is calculated as a sum of the separate subscores divided by 24. If one of the subscores is missing, the mDRS composite score is missing as well. As compared to the official questionnaire, the eCRF allows values of 0 ('normal') for the subscores.

Laboratory

Laboratory safety data measurements that are denoted as smaller/larger than a certain value (e.g. < x.x), will be imputed with this value (e.g. x.x) for calculations of descriptive statistics. Listings will show the value as collected, and a footnote will be added to the summary tables for explanation.

Comments

The following data are either not collected or only collected as free text fields in the eCRF/database or lack relevant information in the database, and it is therefore necessary that these details are added in the programming code manually. The decisions to drive this manual coding may be documented and finalized during the BDRM but can already be maintained/discussed during the course of the trial for efficiency.

- The reason for video unavailability is recorded as free text field, and it needs to be deducted if any of these reasons consider a "technical issue". The sponsor will provide input.
- PATA score missing due to "unable to perform due to physical limitations" is not available as such in the database but needs to be deducted from a free comment field. The sponsor will provide input.
- Age is not collected during the Extension phase and full birthdate is not provided in the Parent study; therefore, the sponsor will provide details which patients turned 13 between Visit 7 and 8, and between Visit 10 and 11.
- SCAFI comments as stated above on SCAFI calculations. The sponsor will provide input to which comments relate to "unable to perform due to physical limitations" and which relate to "not performed for other reason".
- Information to match the supplied bottles and/or sachets of study drug with the returned bottles and/or sachets, to be able to differentiate bottles/sachets used for the Parent phase and the Extension phase to allow appropriate compliance calculations.

Other

Durations, determination of baseline values and handling of missing data will be programmed as stated in the respective analysis sections.

Any other programming conventions that are not foreseen in preparation of this SAP, will be handled when encountered and documented separately.

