5.6.3 Additional secondary endpoints

All additional secondary endpoints will be presented using the mITT and PPS populations, and all individual data will be listed as well. No sensitivity analysis will be applied.

Measurement of Ataxia and Functioning

- SARA total score
- SCAFI total score
 - o 9HPT-D

Clinical Study Reference: IB1001-202

- 9HPT-ND
- o 8MWT
- PATA test

Descriptive statistics will be used to summarize the endpoints above at each visit.

The subscores of the SARA score (gait, stance, sitting, speech disturbance, finger chase, nosefinger test, fast alternating hand movements, heel-shin slide) will also be summarized for each visit using descriptive statistics. Stacked bar charts will be provided per visit, based on the subscores of the total SARA score.

Spaghetti plots of individual patient SARA total scores and the SCAFI total scores versus time will be made as well as a mean or median display versus time, depending upon the distribution, and corresponding two-sided 90% CI at each visit.

The average SCAFI subscores (8MW_avg, 9HPT-D_avg, 9HPT-ND_avg and PATA_avg) as determined according to Section 10.1, following the scoring manual, will also be summarized with descriptive statistics.

The changes in SARA total score, SCAFI total score, the SCAFI subscores (8MW_avg, 9HPT-D_avg, and PATA_avg) between Visit 2 and Visit 4, as well as the changes between Visit 4 and Visit 6 will be analysed using a one-sample t-test or a Wilcoxon Signed Rank test depending on the distribution of the data. The SCAFI subscore 9HPT-ND_avg will only be descriptively summarized in tabular format.

Measurement of Health-related Quality of Life

The results of EQ-5D-5L as well as the EQ-5D-Y will be combined into a 5-digit number presenting the health status of the subject. Frequency tables will be presented per visit for the 5 domains, as well as for the 5-digit number of the EQ-5D-5L and the EQ-5D-Y separately. In addition, EQ-5D-5L and EQ-5D-Y domain percentages will be presented in separate bar charts per visit, with all visits combined into one plot (if possible).

The EQ-VAS score will be summarized by visit using descriptive statistics for patients aged < and \geq 18 years combined. Spaghetti plots of individual patient EQ-VAS scores versus time will be made as well as a mean or median display versus time, depending upon the distribution, and corresponding two-sided 90% CI at each visit.

Measurement of Overall Neurological Status

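### SAP 10.1 read literally puts 3000 s into the tested 9HPT-D average when only the dominant hand fails, but leaves it missing when both hands fail

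*SAP*

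**What the plan says.** SAP 10.1 (SCAFI) averages two trials per hand to give 9HPT-D_avg and 9HPT-ND_avg, then forms 9HPT_recipr as the mean of the two hands' reciprocals. These steps and the substitutions that follow are introduced by "SCAFI total score will be calculated as follows".

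For tests missing through physical limitation, the rule depends on how many hands are missing:
- One hand: "then 9HPT_avg=3000 s for that specific hand".
- Both hands: "when data for both hands are missing, then 9HPT_recipr=1/3000 s". No hand-level average is set.

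In the same list, a failed walk is substituted only on the reciprocal (1/1800), and a failed PATA test gets PATA_avg of 0. Most peg times above 300 s, and walks done with wall or person support, are made missing and then classed as physical limitation.

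SAP 5.6.3 describes the subscore averages "as determined according to Section 10.1, following the scoring manual, will also be summarized with descriptive statistics". It then says that changes in "the SCAFI subscores (8MW_avg, 9HPT-D_avg, and PATA_avg) between Visit 2 and Visit 4", and likewise from Visit 4 to Visit 6, "will be analysed using a one-sample t-test or a Wilcoxon Signed Rank test depending on the distribution of the data". The non-dominant hand is summarized only. SAP 5.3 rules out imputation for additional secondary endpoints unless the analysis section or Section 10.1 specifies it, and uses the data available at each visit.

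**The concern.** The 3000 s figure suits the reciprocal scale on which SCAFI is built. There, 1/3000 is close to zero and simply marks a failure as very slow. The subscore tested in SAP 5.6.3 is an average in seconds, where 3000 is at least ten times any time the SAP accepts as valid.

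The text also treats failures unequally. A patient who loses only the dominant hand counts as an enormous deterioration. A patient who loses both hands has no 9HPT-D_avg and is not counted. What is at stake is the interpretability of the 9HPT-D mean change, its confidence interval and its t-test.

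Such crossings are plausible. Inclusion criterion 6b admits patients on the SARA gait item or on a 9HPT-D time of 20 to 150 s, so a patient can enter without meeting the peg-test limits.

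**Working it through.** The documents give no power, effect size or SD for 9HPT-D, so there is no stated figure to reproduce.

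**Inputs from the documents:** about 36 patients in the mITT and 30 in the PPS (SAP 2.4.1); one-sided 0.05 (SAP 5.1); the substitutes above.

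**Assumptions, not in the documents:** mean change of the other patients -5 s with SD 12 s; range checked, -3 to -20 s with SD 10 to 20 s. Negative values are improvements.

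**1. Size of one entry.** Change = 3000 minus the earlier time. From 300 s: +2,700 s. From 120 s: +2,880 s. From 60 s: +2,940 s.

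**2. Effect on the mean (n=36, 35 others at -5 s).**
- From 120 s: (35 × -5 + 2,880)/36 = 2,705/36 = +75.1 s.
- From 290 s: (-175 + 2,710)/36 = +70.4 s.
- From 60 s, the others would have to improve by 2,940/35 = 84 s on average merely to bring the mean back to zero (2,940/29 = 101 s at n=30).

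**3. Effect on the t-test.** One very large value M gives a mean near M/n and a standard error near M/n, so t is close to +1 whatever M is. Here SD is about 481 s, SE = 481/6 = 80.2 s and t = 75.1/80.2 = 0.94. Simulated t-test power falls from about 80% to 0%.

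**4. Effect on the Wilcoxon test.** Power falls from about 79% to 63%.

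**5. Worked data sets.** The others have mean -5 s and SD 10 s; one patient goes from 60 s to the substitute.

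| | n=36 | n=30 |
|---|---|---|
| Mean without / with that patient | -5.0 / +76.8 s | -5.0 / +93.2 s |
| t-test p for improvement | 0.003 / 0.82 | 0.006 / 0.82 |
| Wilcoxon p | 0.003 / 0.011 | 0.007 / 0.024 |
| Hodges-Lehmann estimate | -5.0 / -4.5 s | -5.0 / -4.4 s |

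If the same patient fails with both hands, the results without that patient stand (n=35 or 29).

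Over the whole assumed range, with starting times of 60 or 150 s, the mean lies between about +60 and +95 s and the t-test p for improvement between 0.77 and 0.83. The p-value for worsening is 0.17 to 0.23, so significant harm is never shown. With SD 10 s, the Wilcoxon test crosses 0.05 only if the others average about -3.0 to -3.6 s (n=36) or -3.3 to -4.1 s (n=30).

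**6. Is 3000 s the cause?** Replace it with 301 s, again from 120 s: (-175 + 181)/36 = +0.2 s. T-test power is still 0% and Wilcoxon power about 63%. The size of the substitute therefore drives the mean. The power loss comes from any large deterioration analysed in seconds.

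**7. Opposite crossing, no true effect.** A dominant-hand failure at Visit 2 with recovery to 120 s at Visit 4 shifts the mean by -2,880/36 = -80 s. The t-test rejects in 0% of runs; the Wilcoxon test rejects in about 8%.

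**8. SCAFI total.** If 3000 s were set for each hand, 9HPT_recipr would be (1/3000 + 1/3000)/2 = 1/3000, the same as the two-hand rule. The total is unaffected.

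**The case against.** The strongest reply concerns scope. The substitution list belongs to the SCAFI total, and the cross-reference to Section 10.1 in SAP 5.6.3 stands in the sentence on descriptive summaries, not in the one on testing. A programmer could reasonably leave 9HPT-D_avg missing for every failure. This stands as a limit: the literal reading is possible but not established. It does not settle the matter, because the same variable name is defined, substituted and tested, and SAP 5.3 makes an exception for Section 10.1.

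A reader might infer that one patient can overturn the 9HPT-D result. That holds for the mean and the t-test only. SAP 5.6.3 allows the Wilcoxon test, and a change near +2,900 s would probably prompt it. That weakens the result without reversing its sign. However, the SAP gives no criterion for the switch, and the descriptive mean is distorted either way.

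A reader might also infer that the opposite crossing could produce a false positive. The t-test does not do so, because the outlier inflates the SD as well; the Wilcoxon error rate rises modestly.

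Nor do the documents support saying that any one-hand failure matters, or that the worst deteriorations drop out in general. Only the dominant hand is tested, and a patient is lost as a deterioration only if both hands fail newly at the later visit. The documents give no frequency for either event.

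Finally, seconds are a defensible unit: Protocol 6.1.2.1 describes the subtests as times.

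**Conclusion.** The point holds as an ambiguity with a harmful literal reading. Under that reading, a dominant-hand-only failure and a two-hand failure are handled in opposite ways, and a single dominant-hand failure makes the mean change in seconds uninformative. The t-test loses essentially all its power and the Wilcoxon test loses a moderate part. The sizes rest on assumed effects and SDs, on one failure among about 36 patients, and on the substitute reaching the tested subscore.

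The consequence is limited. 9HPT-D is an additional secondary endpoint, p-values beyond the primary are indicative, and SAP 5.1 calls those evaluations exploratory. Neither the SCAFI total nor the primary CI-CS analysis is affected. The repair is cheap and worth making.

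**What to change.** In SAP 5.6.3 and 10.1:
1. State that the 3000 s substitute enters no mean or test in seconds.
2. Treat every dominant-hand physical failure the same, whether or not the other hand also fails. Either test the change in 1/9HPT-D_avg with 1/3000 for each such failure, or prespecify the Wilcoxon test with failures given the worst rank. The quantity must be 1/9HPT-D_avg, because 9HPT_recipr combines both hands. If ranks are used, define the rank for a failure at the earlier visit too.
3. Report seconds descriptively without substitution, with the number of failures at each visit.
4. For 8MW, state whether substitutes enter the tested subscore. Keep walks completed with support separate from true inability before applying 1/1800. Otherwise a patient who finished with support is scored as almost immobile, and a change in support between visits becomes a large jump.

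The cost is SAP wording; the reciprocal of each hand's average is already computed for SCAFI. The downside is that the tested unit becomes a rate or a rank instead of seconds. The rate scale does not remove the influence of a failure. In one simulation with assumed baselines of 30 to 150 s, one failure left t-test power at about 55% and Wilcoxon power at about 64%, with the mean still favourable. The t-test figure is sensitive to how the shortest times are modelled.
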